2.5 Participants

During the program, we will interact with following sets of participants: (1) parent caregivers of children with leukemia from the two study facilities, (2) experts (working group) from across Pakistan. The detailed criteria for including or excluding members from each set will be specified further in the description of each phase. All participants must be able to provide consent to participate. These include:

- i. Parent caregivers (biological parents or step-parents) primarily responsible for the daily care of a child diagnosed with leukemia, regardless of the child's treatment stage (diagnosis, active treatment, maintenance, or post-treatment).
- ii. Professionals from disciplines related to the program's goals (pediatric oncology, clinical psychology, psychiatric social work, pediatric nursing, and community health).

2.5.1 Settings

The expert consultations and Delphi will take place online. The sub-studies (interviews, focus groups, and pilot intervention) will be conducted at hospitals, oncology centers, and convenient sites convenient sites agreed upon with parent caregivers.

2.5.2 Recruitment

The literature and professional contacts will inform the recruitment of expert participants. We will recruit parent caregivers of children with leukemia from pediatric oncology facilities in Pakistan (e.g., one in a major urban center like Peshawar and in a secondary city to capture diverse socioeconomic and cultural contexts).

2.6 Step-by-Step Design, Methods and Analyses

We have segmented the development program into four stages to accomplish our goals: (1) Identify the care gap and examine the current evidence on the influence of stage-matched interventions on psychological adaptation of parent caregivers of children with leukemia, (2) construct a model stage-matched intervention, (3) refine the model and draft an intervention, and (4) pilot the draft intervention.

2.7 Stage 1: Gap Definition and Evidence Scoping of the Impact of Stage-Matched Interventions on Psychological Adaptation of Parent Caregivers

2.7.1 Systematic Review of Literature

Objective: To evaluate the impact of stage-matched and psychosocial interventions on psychological adaptation, coping, and distress reduction in parent caregivers of children with leukemia.

Method: A systematic electronic database search will follow the Preferred Reporting Items for Systematic Reviews and Meta-analysis (PRISMA) guidelines. The following key terms and their synonyms will be used: parent caregiver OR mother OR father OR family AND childhood leukemia OR pediatric cancer OR hematologic malignancy AND psychological adaptation OR coping OR distress OR quality of life OR mental health AND stage-matched intervention OR psychosocial support OR psychoeducation OR family intervention. Databases will include MEDLINE, Google Scholar, Cochrane Central Register of Controlled Trials, CINAHL, EMBASE, Web of Science, PsychINFO, Scopus, ClinicalTrials.gov, and the WHO international clinical trials registry. Bibliographies of relevant papers will also be searched to supplement data. Studies that report only child outcomes without parent outcomes will be excluded.

Studies will be included if:

1. They are randomised controlled trials, quasi-experimental studies.
2. Participants are parent caregivers (biological or non-biological) of children (aged 0–18 years) diagnosed with leukemia.
3. Interventions are psychosocial, psychological, or stage-matched targeting parent adaptation.
4. Outcomes include psychological adaptation, coping, distress, anxiety, depression, or quality of life.
5. Studies are published in English.

Analysis: Two independent researchers will screen titles and abstracts. If necessary, the supervisor will settle any disagreements through discussion. The following information will be extracted from the selected studies:

- Study characteristics: number of participants, parent age and gender, child age and leukemia subtype.
- Intervention design features: content and type of intervention, stage-matched components, duration and number of sessions, delivery mode, and follow-up period.

- Comparator: control group intervention (e.g., treatment as usual, waitlist, or alternative support).
- Outcome: data collection points, psychological adaptation measures, coping strategies, distress levels, and method of measurement.

The Cochrane Risk of Bias 2 tool (Cumpston et al., 2019) will be used to assess bias, and the analysed data will be documented in a narrative review. The GRADE (Guyatt et al., 2008) methodology will be employed to evaluate the certainty of evidence, and implementation will be checked against the TIDieR checklist.

The interventions in the included studies will be evaluated based on their impact on parent psychological adaptation, coping, distress, and quality of life, as well as the use of validated outcome measures and their theoretical basis. Studies that report effect sizes will be compared for intervention efficacy. These findings will inform the content and delivery strategies of the stage-matched intervention to be developed.

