2.8 Stage 2: Model Stage-Matched Intervention Development

At this stage, our important goal is to compile a set of modules to promote psychological adaptation in parent caregivers of children with leukemia and provide examples of the implementation of psychosocial interventions in pediatric oncology settings. These will be used to create a model stage-matched intervention. We will conduct various research activities aimed at identifying the key challenges to psychological adaptation and determining the most effective methods for implementing intervention, incorporating insight from experts, parent caregivers, and where appropriate, children with leukemia.

To ensure the stage-matched intervention is rigorous and relevant contextually, the systematic review and expert interview findings will be integrated into each phase of the intervention design. The systematic review will synthesise existing evidence regarding psychosocial support strategies and their effects on parent caregiver adaptation, highlighting key themes such as effective coping techniques, stage-specific needs, and identifying gaps in current approaches. The findings will inform the theoretical foundation of the intervention, specifically the integration of stage-matched models (e.g., transactional family adaptation model) and psychological adaptation frameworks.

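### Section 2.7.1 admits quasi-experimental studies but names only RoB 2, a tool for randomised trials, so confounding in those studies is not adequately appraised

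*Protocol*

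**What the plan says.** Everything needed stands in Protocol 2.7.1, with one link to 2.8.

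- Eligible designs: "They are randomised controlled trials, quasi-experimental studies".
- Items to extract on each study begin with: "Study characteristics: number of participants, parent age and gender, child age and leukemia subtype". The list goes on to intervention features, comparator and outcomes.
- Bias: "The Cochrane Risk of Bias 2 tool" is the instrument. It "will be used to assess bias, and the analysed data will be documented in a narrative review".
- Certainty: the GRADE "methodology will be employed to evaluate the certainty of evidence, and implementation will be checked against the TIDieR checklist".
- Comparison of results: "Studies that report effect sizes will be compared for intervention efficacy".
- Use of the review: "These findings will inform the content and delivery strategies of the stage-matched intervention to be developed". Section 2.8 adds that "the systematic review and expert interview findings will be integrated into each phase of the intervention design".

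**The concern.** The eligibility rule and the bias tool do not fit each other. In a quasi-experimental study the leading threat is that the groups differed before the intervention began. The question for a reviewer is how far the design or the analysis dealt with that. RoB 2 takes randomisation as its starting point and does not ask this question in a form that can be graded.

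At stake is the quality of the Stage 1 evidence appraisal. GRADE takes a risk-of-bias judgement as one of its inputs, so a judgement made with a misfitting tool carries into the certainty rating for any outcome to which quasi-experimental studies contribute. Effect sizes are also to be compared across studies with no stated separation by design. The findings are one of the sources for the content and delivery of the intervention.

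**Working it through.** No arithmetic applies: the point depends on no error rate, effect size or sample size, and the plan gives no figure to reproduce. The check is to set the statements of 2.7.1 beside each other and search the rest of the protocol for anything that fills the gap.

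1. **Are non-randomised studies eligible?** Yes. The first inclusion criterion names quasi-experimental studies next to randomised trials.

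2. **Which tool judges them?** RoB 2. The sentence is not limited to the randomised trials, and no instrument for non-randomised studies is named anywhere in the protocol. This is a stated choice of tool that does not cover all the eligible evidence, which is more than a detail left open. An analysis plan for the pilot trial would not be expected to govern a Stage 1 literature review.

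3. **What can RoB 2 say about a quasi-experimental study?** There are two ways to apply it.
   - The assessor scores the randomisation domain strictly. Every such study is marked down for non-random allocation. This is conservative, but a study with comparable groups and careful adjustment gets the same mark as one with neither.
   - The assessor treats that domain as not applicable and scores the others. Confounding then goes unjudged.

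   The protocol does not say which would happen. Under neither is the degree of confounding control assessed.

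4. **Could the extracted data make up for it?** Not as listed. The items cover participants, intervention, comparator and outcomes. None covers allocation method, baseline comparability or adjustment for confounders.

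5. **Does the GRADE sentence make up for it?** It states no separate handling of randomised and non-randomised evidence. GRADE can take design into account, but it still needs a sound risk-of-bias input within each design.

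6. **How far does the effect reach?** It covers the bias judgement for each quasi-experimental study and any GRADE rating to which such studies contribute. It does not touch ratings based only on randomised trials, and nothing in the Stage 4 pilot (2.10) depends on it.

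**The case against.** The strongest reply is that little harm follows. RoB 2's randomisation domain would flag non-random allocation, so quasi-experimental studies need not pass as equal to randomised trials, and GRADE itself considers study design. The synthesis is narrative and can discuss design in words. The review is also only one input. Section 2.8 combines it with interview findings and sends conflicts between literature and stakeholders to e-Delphi consensus. Section 2.8.2.1 selects trials for the implementation appraisal on methodological rigour, 2.9.1 has caregivers and experts review the model, and 2.11 weights evidence partly by the rigour of data collection. Finally, the number of quasi-experimental studies may be small or zero.

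Most of this stands, and it limits the consequence. It does not remove the mismatch: flagging that allocation was not random is different from judging how serious the confounding is, and later consultation does not repair an appraisal made with the wrong tool.

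A reader might infer three stronger things that the protocol does not support:

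- **That confounding goes wholly unassessed and all GRADE ratings are unreliable.** The randomisation domain gives some signal, and ratings from randomised trials alone are sound in this respect.
- **That GRADE levels decide which components enter the intervention.** Section 2.7.1 judges interventions on impact, validated measures and theoretical basis. It does not make certainty a selection criterion.
- **That quasi-experimental effects will be ranked or pooled with randomised ones.** The text says only that effect sizes will be compared, within a narrative review.

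**Conclusion.** The point holds in a limited form. Section 2.7.1 makes quasi-experimental studies eligible and names only a tool for randomised trials to assess their bias. For those studies the bias judgement is not adequately supported, and the same is true of any GRADE rating that rests wholly or partly on them.

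Severity is minor. The size cannot be given as a number, because the protocol does not say how many quasi-experimental studies there are; if none is found, nothing changes. The conclusion assumes that RoB 2 will be applied to all included studies, as the text reads, and that no other instrument is specified in a separate review protocol that is not at hand.

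**What to change.** Amend 2.7.1 in three places:

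1. **Tool.** Use RoB 2 for randomised trials and ROBINS-I, or an equivalent tool for non-randomised studies, for quasi-experimental studies.
2. **Extraction.** Add allocation method, baseline comparability and adjustment for confounders to the list.
3. **Reporting.** Present effect sizes and GRADE certainty separately for randomised and quasi-experimental studies.

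Restricting eligibility to randomised trials would also remove the mismatch, at the price of a narrower evidence base.

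The cost is a few sentences of text, plus modest extraction and appraisal time for each quasi-experimental study. No participant data are needed. Section 2.14 places Stage 1 in the first two months and the title page gives a start of June 2025, so the review may already be done. In that case only the quasi-experimental studies need extra extraction and re-appraisal, followed by an update of the GRADE ratings to which they contribute.

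### The Stage 1 efficacy comparison admits studies by whether they report an effect size, and the extraction list does not name the statistics needed to derive one for the others (minor).

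*Protocol*

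**What the plan says.** Section 2.7.1 of the protocol describes a systematic review of psychosocial and stage-matched interventions for parent caregivers. Four statements matter here.

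- **Who enters the efficacy comparison.** "Studies that report effect sizes will be compared for intervention efficacy". No sentence says that effect sizes will be computed for other eligible studies or requested from their authors.
- **What is extracted.** The outcome item reads "Outcome: data collection points, psychological adaptation measures, coping strategies, distress levels, and method of measurement". Sample size appears elsewhere in the list: "Study characteristics: number of participants, parent age and gender, child age and leukemia subtype".
- **What covers all included studies.** The sentence just before the comparison rule reads "The interventions in the included studies will be evaluated based on their impact on parent psychological adaptation, coping, distress, and quality of life". The section also plans a Cochrane risk-of-bias assessment with narrative reporting ("will be used to assess bias, and the analysed data will be documented in a narrative review") and GRADE.
- **How the results are used.** "These findings will inform the content and delivery strategies of the stage-matched intervention to be developed". Section 2.8 adds that "the systematic review and expert interview findings will be integrated into each phase of the intervention design".

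**The concern.** Eligibility for the review is set by design, population, intervention, outcome and language. Entry to the efficacy comparison is set by something else, namely whether the authors reported an effect size. If authors are more likely to do so when a result is significant, the compared set is selected partly on the outcome, and the interventions in it will look better on average than the eligible evidence as a whole.

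The extraction list does not close this gap. A standardised effect needs group means and SDs with numbers per arm, or a test statistic or exact p-value with those numbers. None of these is named apart from a number of participants, which is not broken down by arm. The two reviewers could complete the form as listed and still be unable to place a study without a reported effect size beside the others.

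What is at stake is the weight given to one intervention approach over another when the review informs content and delivery.

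**Working it through.** The protocol gives no effect size, power or pooled estimate for this review, so there is no stated figure to reproduce. The check has two parts.

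**1. Section 2.7.1 set against what a standardised effect requires**

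| Needed for a standardised effect | In the extraction list? |
|---|---|
| Numbers per arm | Number of participants is listed; per arm is not stated |
| Group means or change scores | Not named; distress levels might be read as outcome values |
| SDs | Not named |
| Test statistic or p-value | Not named |
| Reported effect estimate | Not named, although the comparison relies on it |

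The list therefore does not specify the necessary statistics. This falls short of showing that no result data would be taken.

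**2. Illustration of the possible size (all inputs assumed)**

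Inputs: true standardised effect d = 0.20; n = 35 per arm, which is the pilot's target arm size in section 2.10 and is not taken from the literature under review; reporting rates as shown below. Each study estimate is normal with mean d and SE = √(2/n) = √(2/35) = 0.239. A result is significant if |estimate| > 1.96 × 0.239 = 0.469.

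Under this model:
- probability of a significant result: P = 0.133
- mean estimate among significant results: 0.567
- mean estimate among the others: 0.144

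Let significant results report an effect size with probability a, and the others with probability b. The mean among reporting studies is

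(a × P × 0.567 + b × (1 − P) × 0.144) / (a × P + b × (1 − P)).

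| a | b | Calculation | Mean among reporters | Excess over 0.20 |
|---|---|---|---|---|
| equal | equal | – | 0.20 | none |
| 0.90 | 0.60 | 0.1427 / 0.6400 | 0.22 | 0.02 |
| 0.90 | 0.40 | 0.1178 / 0.4666 | 0.25 | 0.05 |
| 0.80 | 0.20 | 0.0853 / 0.2799 | 0.305 | 0.105 (about 52%) |

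A second selection model gives a similar picture. Significant favourable results always report an effect size, and all others do so with probability q:

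| True d | q = 1 | q = 0.75 | q = 0.50 | q = 0.25 |
|---|---|---|---|---|
| 0.0 | 0.00 | 0.01 | 0.01 | 0.04 |
| 0.2 | 0.20 | 0.22 | 0.25 | 0.31 |
| 0.4 | 0.40 | 0.43 | 0.47 | 0.53 |
| 0.5 | 0.50 | 0.53 | 0.56 | 0.61 |

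The shift is upward whenever reporting favours significant results. It is zero when reporting is unrelated to the result, and the largest shift in the tables is about 0.13. Its size rests wholly on the reporting rates, which the documents do not give.

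**The case against.** The strongest reply is that the sentence before the rule evaluates all included interventions on their impact. A study without a reported effect size therefore misses one sub-comparison but stays in the narrative review, the risk-of-bias assessment and GRADE. This stands. A reader might infer that null studies disappear from the evidence; the text does not support that.

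A reader might also infer that no result data are extracted, or that effect sizes could never be computed later. That too goes beyond the text. Distress levels may mean outcome values, judging impact presupposes some results, and the published papers remain available. What can be said is that the list does not specify the statistics required.

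A third tempting inference is that module content is chosen from this comparison. Section 2.7.1 says the findings as a whole will inform content and delivery. The protocol also draws on expert consultation (2.7.2), caregiver surveys and interviews (2.8.1), professional interviews (2.8.2.2), and focus groups with an e-Delphi (2.9.1). The implementation model is selected by a separate TOWS appraisal (2.8.2.1).

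It can further be said that no pooled mean is planned, so the illustration measures something the review will not report, and that extraction detail often sits in a review's own form. The first point limits the figures to an indication of direction and scale. The second would carry more weight if the protocol were silent, but it states an entry rule, and that rule is the weak part. Risk-of-bias ratings, GRADE and the trial-registry search can flag or widen the evidence, but they do not put an eligible study back into the comparison.

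**Conclusion.** The point holds as a minor one. The protocol makes entry to its quantitative efficacy comparison depend on the authors' reporting format, gives no rule for the other eligible studies, and does not list the statistics that would allow one.

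Any lean toward favourable findings is a risk and not an established fact, since it requires effect-size reporting to depend on the result and the documents contain nothing on that. On assumed reporting rates and 35 per arm, a true 0.20 would appear as 0.22 to 0.31; with equal reporting it would not move.

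The consequence is confined to one of several inputs to intervention development. The pilot's sample size, randomisation, outcomes and analysis are unaffected.

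**What to change.** In section 2.7.1:

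1. Add to the extraction list, for each outcome and time point, group means and SDs (or change scores with SDs), numbers per arm, test statistics or p-values, and any reported effect estimate.
2. Compute Hedges' g with its confidence interval for every eligible study where it can be derived. Table 3 already names Hedges' g for the pilot, so the two would be on the same scale.
3. Replace the sentence that limits the comparison to studies reporting effect sizes with a comparison on this full set.
4. List the studies for which g cannot be derived, with the direction of their result, so that the narrative shows what the comparison leaves out.

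The cost is a wording change and modest extra extraction time. Selection on reporting format is removed wherever g can be derived and is made visible where it cannot.

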2.7.2 Gap Identification from Expert Professional's Experience

Objective: To gain insight from experts in the fields of pediatric oncology, clinical psychology, psychiatric social work, and pediatric nursing about the psychological adaptation challenges faced by parent caregivers of children with leukemia and potential stage-matched solutions to address these challenges.

Method: Two structured discussion meetings will be held. Each participant will share their responses to these questions: Could you outline the main areas of knowledge that are lacking in your professional opinion regarding parent caregivers of children with leukemia? What difficulties could arise if parent caregivers experience poor psychological adaptation? What potential stage-matched solutions would you propose for addressing these challenges across different phases of the child's treatment (diagnosis, active treatment, maintenance, relapse, or post-treatment)? The experts will be advised to focus on their direct research and clinical experience.

Participants: Expert professionals selected through a quick review of literature and recommendations from practitioners in the field will be invited for an expert consultation. These experts will cover various disciplines and will come from across Pakistan, including both urban and rural healthcare settings.

Analysis: Thematically we will analyse the experts' responses to identify priority gaps.

2.8 Stage 2: Model Stage-Matched Intervention Development

At this stage, our important goal is to compile a set of modules to promote psychological adaptation in parent caregivers of children with leukemia and provide examples of the implementation of psychosocial interventions in pediatric oncology settings. These will be used to create a model stage-matched intervention. We will conduct various research activities aimed at identifying the key challenges to psychological adaptation and determining the most effective methods for implementing intervention, incorporating insight from experts, parent caregivers, and where appropriate, children with leukemia.

To ensure the stage-matched intervention is rigorous and relevant contextually, the systematic review and expert interview findings will be integrated into each phase of the intervention design. The systematic review will synthesise existing evidence regarding psychosocial support strategies and their effects on parent caregiver adaptation, highlighting key themes such as effective coping techniques, stage-specific needs, and identifying gaps in current approaches. The findings will inform the theoretical foundation of the intervention, specifically the integration of stage-matched models (e.g., transactional family adaptation model) and psychological adaptation frameworks.

Additionally, insights from expert interviews with pediatric oncologists, psychologists, nurses, and parent caregivers will offer practical perspectives on implementation challenges and cultural nuances in Pakistan. Interviews may identify specific barriers, such as stigma, financial stress, family dynamics, and gender roles, which can be addressed through tailored psychoeducational components. Thematic analysis of interview data will enhance intervention delivery methods and ensure content accessibility across diverse literacy levels and linguistic backgrounds. The research team will utilise the Intervention Mapping framework to synthesize these inputs, converting evidence into actionable behavioural objectives, such as enhancing problem-focused coping, seeking social support, and employing emotion regulation techniques, and employing theory-based change methods, including role-playing exercises, guided imagery, and peer support. Discrepancies between the literature and stakeholder feedback will be addressed through consensus in the e-Delphi process, ensuring that the final intervention integrates evidence-based rigour with practical feasibility. This iterative approach guarantees that the final intervention

maintains a balance between evidence-based rigour and real-world feasibility, rendering it both theoretically strong and practically suitable for the needs of parent caregivers of children with leukemia in Pakistan.

2.8.1 Identifying the Modules and Intervention Implementation from the Viewpoints of Parent Caregivers

Objective: To establish the psychological adaptation challenges of parent caregivers of children with leukemia from the perspectives of the caregivers themselves and, where appropriate, their children.

Method: This will be a mixed-methods research at the two study sites. The quantitative part will be a researcher-administered survey of parent caregivers of children with leukemia. The questionnaires will include: (1) sociodemographic information, (2) Psychological Adaptation Scale (PAS), (3) Caregiver burden scale, (4) Depression Anxiety and Stress Scale (DASS-21), (5) Perceived Social Support Questionnaire).

The qualitative study will consist of semi-structured interviews with parent caregivers of children with leukemia. This will attempt to identify the psychological adaptation challenges, coping mechanisms, and support needs across different treatment stages (diagnosis, active treatment, maintenance, relapse, bereavement, or survivorship).

Sample size: We will recruit 20 parent caregivers from each study facility (n = 40).

Participants: Parent caregivers (biological parents or guardians) of children diagnosed with leukemia, regardless of the child's treatment stage.

Analysis: Descriptive and quantitative methodologies will be used to analyse questionnaire data to determine the psychological adaptation challenges and their correlates. Transcribed audio recordings will undergo thematic analysis (Braun and Clarke, 2006). Drawing upon existing literature and theoretical basis, a research inquiry will be formulated to establish a framework for identifying pertinent data. The subsequent phase of data coding will entail category extraction from the data determined to be relevant to the research inquiry. Significant parent caregiver areas of need will be identified through an analysis that examines the main categories and discussion topics.

2.8.2 Identifying the Modules and Intervention Implementation from the Viewpoints of Professionals

We will use semi-structured interviews to elicit experts' viewpoints on the most appropriate intervention content and mode of implementation for stage-matched psychological adaptation support.

